15.1 Variables and derivations

In eCRF "Concomitant Medications: General Use" form we are capturing the concomitant medication related data.

Concomitant medications are defined as any medication taken after first administration of the IMP till the end of the trial.

All medications will be coded using the WHO-DD, dated (refer to DMP for dictionary date) All concomitant therapies that was originally mapped using the WHO Drug Dictionary in the ClinTrial database will be further classified using Anatomical Therapeutic Chemical (ATC) codes for reporting purposes.

The following parameters will be summarised separately for the subject's with concomitant medication and Special Interest Hyperglycaemia related concomitant medication:

- Number of subjects with at least one concomitant medication and Special Interest Hyperglycaemia related concomitant medication
- Number of subjects for each concomitant medication and Special Interest Hyperglycaemia related concomitant medication by ATC and PT.

The following variables will be listed concomitant and other medications:

- Subject Number
- Medication class/ Standardized medication name/ Reported term
- Dose and unit
- Frequency
- Route
- Start date of medication
- End date of medication

Rescue Medication:

The rescue medication related data will be captured in "Concomitant Therapy: Special Interest Hyperglycaemia" special form in eCRF.

The rescue medication we will identify using following variables:

- Date of first dose administration
- First Rescue medication date

Derivations:

All concomitant medication and Special Interest Hyperglycaemia related concomitant medication, which are identifies as follows:

 If start date of concomitant medication >= Date of first dose administration, then we will consider it as "concomitant medication".

For identification of rescue medication visit wise we will use the following derivation:

(First Rescue Medication Date – Date of First Dose Administration) +1

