### 6.1. Inclusion Criteria

Subjects are eligible to be included in the study only if they meet all of the following criteria at screening:

- [1] have T2DM based on the disease diagnostic criteria from the World Health Organization (WHO) classification ([Appendix 6](#)) for at least 6 months before screening
- [2] men or non-pregnant women aged more than 18 years and less than 75 years at the time of screening
- [3] have been receiving GLP-1 RA or  $\geq 2$  OAMs at stable doses for 90 days prior to Visit 1
- [4] have an HbA1c level  $\geq 7.0\%$  and  $< 11.0\%$
- [5] have never been treated with insulins except for short term treatment of acute conditions up to a maximum of 14 days
- [6] are able and willing to provide signed informed consent to participate in this study in accordance with local regulations

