## 7. Treatments

### 7.1. Treatments Administered

Subjects will receive Basaglar QD at bedtime. The starting dose will be 10 units. Subjects can self-titrate as outlined in [Table ABEX.4](#) once or twice weekly until FBG is lowered to <100 mg/dL (5.6 mmol/L). In case of hypoglycemia, the dose can be reduced by 4 units. Subjects will continue their pre-study anti-diabetic medications at the prescribed dosage throughout the study except for risks described in Section [7.7](#). It is recommended that doses of anti-diabetic medications being taken by the subjects is stable for 90 days prior to enrolling them in this study. However, the investigator can recommend that these doses be optimized to maximum tolerated dose during 2 weeks of the screening period. If the target FBG levels are not achieved at Visit 2, the subjects are included in the study and Basaglar is initiated.

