## 7.7. Concomitant Therapy

All combination of OAMs or GLP-1 RAs are allowed in the protocol and can be continued with Basaglar. Subjects need to be on GLP-1 RA or at least 2 OAMs at the time of entering the study. For subjects on thiazolidinediones, the investigator may consider reducing the dose or discontinuing it, if there is risk of fluid retention in the subject or complaint of shortness of breath during rest. For subjects on sulphonylureas, the investigator may consider to modify the dose in cases of hypoglycemia.

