#### **10.3.1.3. Concomitant Therapy**

Concomitant medications, including previous therapy for diabetes, will be summarized by different categories and treatment group using the FAS population. All concomitant therapies that was originally mapped using the WHO Drug Dictionary in the ClinTrial database will be further classified using Anatomical Therapeutic Chemical codes for reporting purposes.

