4.1 Design overview

This is a multicenter, open-label, single-arm, phase 4 study to assess the safety of Basaglar in insulin-naïve subjects with T2DM in India. The study period consists of a screening period (Week -2 to Week 0), a treatment period (Week 0 to Week 24), and a safety follow-up visit at Week 28.

Treatment period contains Week 0 to Week 12 will be the titration phase followed by the maintenance phase till Week 24. Approximately 295 subjects will be screened as per the inclusion and exclusion criteria mentioned in Sections 6.1,(in protocol) and 6.2,(in protocol) respectively, so that 250 subjects can be enrolled in the study, with a target to have a minimum of 200 subjects completing the present study. Subjects will be screened at Visit 1 and eligible subjects will be administered with Basaglar once daily (QD) from Visit 2 for a period of 24 weeks. In this study, we would seek to understand the safety of this drug in the local Indian population in accordance with the biosimilar guidelines of India. Subjects will self-administer Basaglar once daily at bedtime (starting dose will be 10 units). Subjects can self-titrate (as per outlined in table 4.1) 2-4 units once or twice in weekly until FBG levels are lowered to <100 mg/dL (5.6 mmol/L). In case of hypoglycemia, the dose can be reduced by 4 units. Subjects will continue their pre-study anti-diabetic concomitant medications.

This is a single-arm study and enrolled subjects will be treated with Basaglar using a self-titration scheme as outlined in below table 4.1.

| Fasting Blood Glucose (mg/dL) | Fasting Blood Glucose (mmol/L) | Dose Adjustments (Units) |
|-------------------------------|-----------------------------------|--------------------------|
| <80 | <4.4 | -2 |
| 80-100 | 4.4-5.6 | 0 |
| 101-130 | 5.6-7.2 | +2 |
| 131-160 | 7.3-8.9 | +4 |
| 161-190 | 8.9-10.6 | +6 |
| >190 | >10.6 | +8 |

Table 4.1

No randomization will be performed as this is a single-arm study. The sample size was calculated assuming a 15% screen failure rate, with a target to have a minimum of 200

subjects completing the study. No interim analyses and/or sample size re-estimation are planned to be performed.

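### The derivation in SAP 15.1 contradicts the section's own definition of concomitant medication and drops background antidiabetic therapy from the planned tables

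*SAP*

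**What the plan says.** SAP 15.1 contains two rules for the same variable. The definition in the text is: "Concomitant medications are defined as any medication taken after first administration of the IMP till the end of the trial". The derivation given to the programmer is: "If start date of concomitant medication >= Date of first dose administration, then we will consider it as" concomitant medication. It is introduced by "All concomitant medication and Special Interest Hyperglycaemia related concomitant medication, which are identifies as follows", so it governs both the general form and the special hyperglycaemia form. SAP 15.2 then builds frequency tables by ATC and PT, plus a listing, for the FAS and PPS.

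On background therapy:
- Protocol 6.1, criterion 3, requires a GLP-1 RA or two or more "OAMs at stable doses for 90 days prior to Visit 1".
- Protocol 7.7 repeats the requirement: "Subjects need to be on GLP-1 RA or at least 2 OAMs at the time of entering the study".
- Protocol 7.1 states: "Subjects will continue their pre-study anti-diabetic medications at the prescribed dosage throughout the study", with exceptions described in 7.7.
- SAP 4.1 itself calls these drugs concomitant: "Subjects will continue their pre-study anti-diabetic concomitant medications".

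On reporting, Protocol 10.3.1.3 states: "Concomitant medications, including previous therapy for diabetes, will be summarized by different categories".

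**The concern.** The definition and the derivation disagree for every drug that was started before first dose and continued afterwards. By design that is the background antidiabetic regimen of the whole study population. Programming normally follows the derivation, so the tables would omit what the text and SAP 4.1 call concomitant.

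This is a single-arm study whose primary endpoint is the incidence of hypoglycaemia, and all combinations of OAMs and GLP-1 RAs are allowed. Protocol 7.7 connects one class, sulphonylureas, with hypoglycaemia by letting the investigator consider a dose change when it occurs. With no comparator arm, a reader needs the background mix as context for the incidence.

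No other planned table supplies it. The baseline characteristics in SAP 11.1 do not include diabetes therapy. SAP 14 mentions treatment history in its title but specifies only MedDRA-coded medical history. SAP 15 has no category for prior medication, and Protocol 10.3.7 plans no subgroup analyses.

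**Working it through.** No sample size, power or precision figure in either document depends on this flag, so there is no stated figure to reproduce. The check is one of date logic.

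**Step 1: latest start of a qualifying background drug.** Inputs: 90 days of stable dose before Visit 1 (Protocol 6.1); Visit 1 at Week -2 and Visit 2 at Week 0 with a window of 3 days either way (Schedule of Activities); first dose at Visit 2 (Protocol 5.1.1).

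Latest start relative to first dose = -(90 + days from Visit 1 to Visit 2)

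- Gap of 11 days: -(90 + 11) = -101
- Gap of 14 days: -(90 + 14) = -104
- Gap of 17 days: -(90 + 17) = -107

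The derivation needs a value of 0 or more, so it is false in all three cases. Protocol 7.1 also allows doses to be optimised during the two screening weeks. A record created for that reason still starts before first dose and fails too.

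**Step 2: both rules applied to illustrative records** (days from first dose, with 0 = first dose; the records are invented to test the rules):

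| Record | Start | End | Derivation | Text definition |
|---|---|---|---|---|
| OAM, stable | -400 | ongoing | no | yes |
| Sulphonylurea stopped at Week 8 | -200 | 56 | no | yes |
| OAM, dose raised in screening | -10 | ongoing | no | yes |
| OAM stopped before first dose | -300 | -5 | no | no |
| OAM, on-study dose change entered as a new record | 40 | ongoing | yes | yes |
| New rescue drug | 60 | ongoing | yes | yes |

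The rules differ in the first three rows, which are the usual forms of continuing background therapy. They agree on drugs stopped earlier and on records started later.

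**Step 3: what the tables would then contain.** Under the derivation, a background drug can appear only through a later-dated record, as in row five. The table would then count background therapy mainly in subjects whose regimen changed. For sulphonylureas, Protocol 7.7 gives hypoglycaemia as a reason for such a change. The counts would therefore be selective as well as too low.

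**Step 4: incomplete dates.** A record without a usable start date cannot be tested against the rule. SAP 8.2 leaves missing data outside its listed cases unimputed, and the partial-date algorithm in SAP Section 24 covers adverse events only.

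**The case against.** The strongest counter-argument concerns consequences, and most of it stands.

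- A reader might infer that the report would show nothing of what Basaglar was combined with. The documents do not support that. SAP 15.1 also plans a by-subject listing of concomitant and other medications with dose, start date and end date, and does not say that it is limited to flagged records. SAP 15.2 describes it as a listing of concomitant medication, so the point is open. The loss is certain only for tables built on the flag.
- A reader might infer that the primary incidence could not be interpreted. That is too strong. SAP 19.2.1 estimates one proportion with a Clopper-Pearson interval and uses no medication flag. What is lost is tabulated context.
- A reader might infer that no subject's background therapy would appear. Dose changes entered as new records can bring a drug back in, depending on eCRF completion rules that the documents do not give. The 90-day criterion also dates only the qualifying drugs, not every antidiabetic drug a subject takes.
- A record count can only be illustrative. Assuming 250 enrolled and one record per drug, the minimum runs from 250 × 1 = 250 (all on a GLP-1 RA alone) to 250 × 2 = 500 (all on two OAMs). The documents give neither the mix nor the record structure.

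None of this removes the contradiction within SAP 15.1 or the departure from Protocol 10.3.1.3.

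**Conclusion.** The point holds for the frequency tables. SAP 15.1 states a rule that does not implement its own definition. It excludes the original records of the qualifying background therapy of every eligible subject, all started at least about 101 to 107 days before first dose. The ATC/PT tables would be selectively incomplete and would not deliver the summary of previous diabetes therapy that the protocol requires. Protocol 10.3.1 asks for changes of method to be justified in the SAP or the study report; the SAP gives no justification here, so this reads as an oversight.

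No estimate, confidence interval or analysis set changes. The data are collected and recoverable, so this should be corrected before programming but does not threaten the primary analysis.

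The conclusion assumes that the derivation is coded as written and that each drug's recorded start date is its true start.

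**What to change.** Amend SAP 15.1 and 15.2 as follows.

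1. For the general concomitant medication form, derive concomitant = start on or after first dose, OR (start before first dose, or start date missing or partial) AND (ongoing, or ended on or after first dose).
2. Classify drugs that ended before first dose as prior medication and report them as such.
3. Add a summary of background antidiabetic therapy by ATC class, to meet Protocol 10.3.1.3.
4. State how missing or partial medication start and end dates are handled.
5. Keep rescue identification on its own rule (new therapy after first dose, from the special hyperglycaemia form), so that widening the flag does not count background drugs as rescue. The rules in SAP 20.1.4, 20.1.6 and 20.1.8 that set values to missing use start dates from that form and should not be altered by this change.
6. Confirm from the eCRF which form holds background antidiabetic drugs, so that the new table draws on the right source.

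The cost is SAP wording, a small code change and one table. No new data collection and no change to sample size or clinical conduct is needed.

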15.2 Analysis

| Population: | FAS and PPS |
|-----------------|--|
| Stratification: | Table: by ATC and PT |
| | Listing: By subject |
| Statistics: | Concomitant medication and Special Interest |
| | Hyperglycaemia related concomitant medication will be |
| | summarized separately as (frequency, percentages) for |
| | table and listing will be presented for concomitant |
| | medication and Special Interest Hyperglycaemia related |
| | concomitant medication. |
| | The rescue medication will be summarized as (frequency |
| | and percentage) by visit (i.e. Week 4, 8, 12, 16, 20 and 24) |
| | for FAS population. |
| | By using formula mentioned in derivation section for rescue |
| | medication, we will get the Day at which the rescue |
| | medication will be started per subject, then we will convert |
| | these days to respective visits. |

e.g. if, subject in the trial who needs rescue medication on day 30 (Day 30 is calculated using derivation mentioned above for rescue medication) then this subject will be counted under week 4 visit (as Day 30 comes under the week 0 to week 4 visit).

Denominators for "n" are per visit, for "n-cumulative" it will be the number of subjects with at least 1 visit up to respective visit.

16. Adverse events

16.1 Variables and derivations

Adverse Events (AEs) will be coded using MedDRA central coding dictionary, Version (refer to DMP for dictionary version).

Adverse events (AE) and Serious adverse event (SAE) are defined as events that are reported after the signing the inform consent form (ICF).

Treatment-emergent adverse events (TEAEs) are defined as events that are newly reported after the first study drug treatment or are reported to have worsened in severity after the first study drug treatment. In the case where it is impossible to define an AE as treatment-emergent or not, the AE will be classified by the worst case assigned, i.e. a TEAE.

In section 24 Appendix 2 the algorithm is given for calculation of partial date imputation for adverse events (AEs) and it will be used for partially missing adverse event start and end date imputation.

Each adverse event will be described by following in listing:

- Subject Number
- Description (AE term) i.e. System organ class/ Preferred terms / Reported terms
- Duration (start and end dates)
- Severity of event
- Relationship to the investigational product
- Relationship to non-study drug treatment
- Relationship to the study procedure
- Action taken with the study treatment
- Outcome
- Whether SAE or not

Each serious adverse event will be described by following in listing:

Subject Number

CONFIDENTIAL CS.BS.01.00 TPL-1.0: Statistical Analysis Plan Template Page 41 of 85

- Description (SAE term) i.e. System organ class/ Preferred terms / Reported terms
- Duration (start and end dates)
- Seriousness criteria
- Toxicity grade
- Severity
- Causality
- Outcome

The following parameters will be summarised for the subject's adverse events as mentioned in eCRF

- Number of participants with at least one TEAEs
- Number of participants with at least one drug related TEAEs
- Number of participants with at least one serious TEAEs
- Number of participants with at least one drug related serious TEAEs
- TEAE by Severity
- TEAEs leading to Death
- Drug-related TEAEs leading to Death
- TEAEs leading to early withdrawn of study
- Injection site Adverse events

Derivations:

- If adverse event start date ≥ Study drug administration start date, then we will consider it as TEAE.
- If adverse event start date ≥ Study drug administration start date and adverse event related to study treatment = "YES", then we will consider it as drug related TEAEs.
- If adverse event start date ≥ Study drug administration start date and adverse event serious = "YES", then we will consider it as serious TEAEs.
- If adverse event start date ≥ Study drug administration start date and adverse event serious = "YES" and adverse event related to study treatment = "YES", then we will consider it as drug related serious TEAEs.

Page 42 of 85

- If adverse event start date ≥ Study drug administration start date and subject's primary reason for discontinuation = "DEATH", then we will consider it as TEAEs leading to Death.
- If adverse event start date ≥ Study drug administration start date and subject's primary reason for discontinuation = "DEATH" and adverse event related to study treatment = "YES", then we will consider it as Drug-related TEAEs leading to Death.
- If adverse event start date ≥ Study drug administration start date and subject's primary reason for discontinuation = "ADVERSE EVENT", then we will consider it as TEAEs leading to early withdrawn of study.
- If the question "were the injection site reaction(s) recorded in AE form" is answered as "YES" in eCRF "Injection Site Reaction" form, then we will consider it as Injection site Adverse events

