#### 10.3.2.4. Adverse Events Analyses

Adverse events will be listed by

- subject
- system organ class (SOC)
- Medical Dictionary for Regulatory Activities® preferred term (PT)
- severity, and
- relationship to the study disease, drug, device, or procedure for all subjects.

Adverse events (including injection site reactions and neoplasms) will be summarized as TEAEs for the FAS population. Treatment-emergent AEs are defined as events that are newly reported after the first study drug treatment or are reported to have worsened in severity after the first study drug treatment. The proportion of subjects experiencing each TEAE will be presented by PT, SOC, and treatment group. The proportion of subjects experiencing each TEAE that is assessed as possibly related to the study disease, drug, or procedures will also be summarized. Treatment-emergent AEs will be summarized by PT within SOC and by PT by decreasing frequency.

All SAEs will be listed by subject and summarized by treatment as counts and percentages. Similar analyses will be performed for discontinuations due to AEs.

All AEs analyses will be repeated for the PPS population.

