20.1 Variables and derivations

20.1.1 Serious adverse events (SAEs) and treatment-emergent adverse events (TEAEs)

Variables:

- First Study drug administration Date
- Serious AE start Date
- Inform consent date
- Adverse Event Serious i.e. (AESER)

Derivations:

- If Adverse Event Serious i.e. (AESER) = "YES" and Serious AE start Date >= Inform consent date, then we will consider it as serious adverse event (SAE)
- If AE start Date >= First Study drug administration date, then we will consider it as treatment-emergent adverse events (TEAEs)

20.1.2 Rates per 30 days and per subject year of total hypoglycemic events (symptomatic or asymptomatic)

Variables:

- What was the blood glucose level (mg/dL) prior to treating the event? (In eCRF "Hypoglycemia Events" form)
- Were signs/symptoms of hypoglycemia present, other than the blood glucose reading? (In eCRF "Hypoglycemia Events" form)
- Hypoglycemic event start date
- Date of Visit 2 (Week 0)
- Date of Visit 8 (Week 24)
- Date of Visit 9 (Week 28)
- Date of first IMP dose administration (In eCRF "Exposure" form)
- Date of last IMP administration (In eCRF "End of Study" form)

Derivations:

- The symptomatic and asymptomatic i.e. total hypoglycemic events will be identified based on derivation mentioned in section 19.1.1.
- Hypoglycemic event start date ≥ Date of Visit 2 (Week 0) and Hypoglycemic event start date ≤ Date of Visit 8 (Week 24) for accessing the hypoglycemic events from Day 0 to week 24.
- Hypoglycemic event start date ≥ Date of Visit 2 (Week 0) and Hypoglycemic event start date ≤ Date of Visit 9 (Week 28) for accessing the hypoglycemic events from Day 0 to week 28.

The formula used for calculation for rates per 30 days and per subject year (365.25 days) of total hypoglycemic events mentioned below:

The rate of hypoglycemic events per 30 days $= \frac{\text{"The total number of events between the time points"}}{\text{"Actual number of days between the time points"}} * 30$ The rate of hypoglycemic events per year (365.25 days) $= \frac{\text{"The total number of events between the time points"}}{\text{"Actual number of days between the time points"}} * 365.25$ Offset variable for per 30 $= log \left(\frac{\text{"The Duration of treatment exposure"}}{30}\right)$ Offset variable per year $= log \left(\frac{\text{"The Duration of treatment exposure"}}{365.25}\right)$

Note: For the duration of treatment exposure see formula mentioned in section 12.1

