23.9 Presentation of visits

- Visit 1 (Week -2)
- Visit 2 (Week 0)
- Visit 3 (Week 4)
- Visit 4 (Week 8)
- Visit 5 (Week 12)
- Visit 6 (Week 16)
- Visit 7 (Week 20)
- Visit 8 (Week 24)
- Visit 9 (Week 28)

24. Appendix 2: Partial date conventions for adverse events.

The whole missing date will not be imputed for this study and only partial date imputation will be performed. Conventions pertaining to partial dates are presented in Table 24.1.

| Table 24.1: Algorithm for Partial Date I | mputation of Adverse Event |
|--|----------------------------|
|--|----------------------------|

| ADVERSE EVENT | MISSING | IMPUTATION |
|---------------|---------------------|--|
| Start Date | Day | If AE start month = Treatment start month and AE start year = Treatment start year, then AE start day= Treatment start day Otherwise AE start day=01 |
| | Day and Month | If AE start year = Treatment start year, then AE start day and month = Treatment start day and month Otherwise AE start day = 01 and AE start month=Jan |
| | Day, Month and Year | No imputation will be performed |
| End Date | Day | If AE end month = Date of study completion/discontinuation month and AE end year = Date of completion/discontinuation year, then AE end day = date of completion/discontinuation day Otherwise AE End day = Last day of respective month, used if this does not result in a date after the subject's trial exit date (e.g. death) in which case the trial exit date will be used |
| | Day and Month | If AE end year = Date of study completion/discontinuation year, then |

CONFIDENTIAL CS.BS.01.00 TPL-1.0: Statistical Analysis Plan Template

Page 84 of 85

AE End day and month = Date of study completion/discontinuation day and month Otherwise AE end day = Last day of respective month and AE end month = Last month of the year, used if this does not result in a date after the subject's trial exit date (e.g. death) in which case the trial exit date will be used

Day, Month and Year No imputation will be performed

CONFIDENTIAL CS.BS.01.00 TPL-1.0: Statistical Analysis Plan Template

Page 85 of 85

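### The TEAE derivations use start date alone and omit the worsening and worst-case parts of the SAP's own definition, while Table 24.1 can turn a resolved pre-dose event into a TEAE

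*SAP*

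**What the plan says.** SAP 16.1 gives the definition in words. It covers "events that are newly reported after the first study drug treatment" and also events that "are reported to have worsened in severity after the first study drug treatment"; Protocol 10.3.2.4 has the same two limbs. SAP 16.1 alone adds a rule for events that cannot be placed either way: "the AE will be classified by the worst case assigned, i.e. a TEAE".

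The derivations later in SAP 16.1 reduce this to one comparison: "If adverse event start date ≥ Study drug administration start date, then we will consider it as TEAE". The same start-date condition is then built into the derivations for drug-related, serious, drug-related serious, fatal, drug-related fatal and withdrawal TEAEs. Injection-site events are the exception, since they are picked up from an eCRF question.

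SAP 20.1.1 repeats the start-date rule for the secondary endpoint. The variables it lists are the first-dose date, the serious AE start date, the consent date and the seriousness flag. SAP 20.2.1 says that SAEs and TEAEs are identified by that derivation.

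SAP Appendix 2, Table 24.1, leaves a wholly missing date unimputed. If the day is missing and the month and year match treatment start, "then AE start day= Treatment start day". If day and month are both missing and the year matches, both are taken from treatment start. The AE end date is not consulted.

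**The concern.** A programmer working from the derivations would produce a different TEAE set from one working from the definition a few lines above. The start-date rule has no term for worsening, and the variables listed in 20.1.1 include neither a severity change nor an AE end date, so neither the worsening limb nor the worst-case rule can be applied from them. A missing date in SAS compares as smaller than any date, so an undated event fails the comparison, which is the reverse of the worst-case rule.

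Such records can arise. Protocol 9.2.1 has all AEs recorded from consent, about two weeks before first dose, so events with a pre-dose start will be in the data. SAEs and TEAEs are the first-listed secondary endpoint of a study whose purpose is safety, and several sub-categories carry the same condition. A few misplaced events could alter the count for a rare or serious term.

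**Working it through.** The plan states no figure on this point, so the check is one of logic: apply the derivation and the definition to the same records and compare.

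Inputs:
- Derivation (SAP 16.1, 20.1.1): TEAE if start date ≥ first-dose date. A missing date fails the comparison.
- Definition (SAP 16.1): TEAE if new after first dose, or worsened after first dose, or impossible to place.
- Imputation (SAP Table 24.1): as described above.
- Illustrative first dose: 15 January 2020.

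| | Record | Start after Table 24.1 | Derivation | Definition |
|---|---|---|---|---|
| 1 | New event, 24 Jan | 24 Jan | TEAE | TEAE |
| 2 | Starts 8 Jan, does not worsen | 8 Jan | not | not |
| 3 | Starts 8 Jan, worsens on drug, kept as one record | 8 Jan | **not** | **TEAE** |
| 4 | Worsening entered as its own event, 3 Feb | 3 Feb | TEAE | TEAE |
| 5 | January 2020, day missing | 15 Jan | TEAE | TEAE |
| 6 | 2020, day and month missing | 15 Jan | TEAE | TEAE |
| 7 | Start date wholly missing | missing | **not** | **TEAE** |
| 8 | January 2020, day missing, known end 10 Jan | 15 Jan | **TEAE** | **not** |

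Records 1 to 7 test the start-date rule: 5 of 7 agree, and records 3 and 7 do not. Record 8 tests the imputation. Its imputed start falls five days after its known end, so an event that was over before dosing is counted as a TEAE. The worst-case rule does not excuse this, because the end date makes the event classifiable. Table 24.1 keeps imputed end dates from running past trial exit, but has no matching limit on imputed start dates.

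With the flag proposed below, record 3 becomes a TEAE through worsening, record 7 becomes a TEAE because no end date rules it out, and record 8 has its start held at 10 January and is not a TEAE. All eight then agree with the definition.

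On size, the documents give no count of pre-dose AEs, worsened AEs or missing dates. As a pure assumption, suppose 5% to 10% of the 250 planned subjects have an AE starting in screening, 10% to 20% of those worsen on drug, and every worsening stays on the original record:
- low: 250 × 0.05 × 0.10 = 1.25 subjects
- high: 250 × 0.10 × 0.20 = 5 subjects, or 5/250 = 2%

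If each worsening is entered as a new event (record 4), the number is 0. The range to carry is therefore 0 to about 5 for worsening. Nothing in the documents supports an estimate for wholly missing or partial dates.

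**The case against.** The strongest reply is that the SAP does not actually exclude these events. The TEAE bullets are prose without an otherwise-not branch, whereas the population flags in SAP 6.1 and 6.2 do set everyone else to N. The worst-case sentence in 16.1 is itself a rule, and it covers an undated event. On this view the SAP needs reconciling, and the SAS comparison matters only to a programmer who overlooks that sentence. This stands in part: the result is a conflict within the SAP rather than a clear exclusion. But 20.2.1 sends the programmer to 20.1.1, where the start-date rule appears without the worst-case sentence, so the narrow rule is the one most likely to be programmed.

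Second, Protocol 9.2 has sites record any change in a preexisting condition as an AE. If that record is dated at the change, it passes the rule. This also stands, as a condition: the documents do not say whether a new record is opened, what start date it takes, or what happens to an AE that began in screening and later worsens.

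Third, a reader might infer that an event becoming serious on drug vanishes from the safety report. It does not. SAEs are identified from the consent date in 20.1.1 and have their own summary in 16.2.9, so a dated post-consent SAE still appears there. It would be absent only from the serious-TEAE categories. An undated serious event is different, because read literally it fails the consent-date comparison as well.

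**Conclusion.** The derivations in SAP 16.1 and 20.1.1 are narrower than the definition they are meant to implement. Taken literally, they miss worsening kept on a pre-dose record and events with a wholly missing start date, and Table 24.1 can add an event that ended before dosing. The wording mismatch is certain. Its effect on the tables cannot be computed, is probably small, and may be zero for worsening, depending on how sites record it. The primary endpoint is not touched.

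Two stronger readings are not supported. A reader might conclude that these events disappear from every TEAE table, but injection-site events are identified by another route, and partial dates matching the dosing month or year are imputed and kept. A reader might also see the missing-date problem as a departure from the protocol. The worst-case rule is in the SAP only, so that part is internal to the SAP; only the worsening limb is shared with Protocol 10.3.2.4.

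**What to change.** Define one TEAE flag in SAP 16.1, and refer to it from 20.1.1, as any of:
- start on or after first dose;
- start before first dose, with worsening after first dose (an increase in severity, or becoming serious);
- start date wholly missing, unless the end date is before first dose.

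Seriousness is not severity, so the second limb should name both. SAP 16.1 and Protocol 10.3.2.4 speak only of severity, while Protocol Appendix 1 describes a TEAE more broadly as worse than the pretreatment state. The SAP should say that it follows the broader reading.

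Use this flag in every start-date-based sub-category. Add to Table 24.1 that an imputed start date may not fall after a known AE end date. State how worsening is recorded in the eCRF, as a new record with its own start date or as a severity change on the existing one, and add the variables needed to 20.1.1. In the same pass, say how the SAE rule in 20.1.1 treats a missing start date.

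The cost is minor SAP and programming work. The one real dependency is that worsening must be identifiable in the AE records. The SAP's AE listing shows a single severity item per event, so this should be checked against the eCRF before the flag is finalised.
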